5. STUDY ASSESSMENT

5.1. Efficacy Assessments

5.1.1. Surgical Site Signs and Symptoms

The following signs and symptoms of the surgical site will be evaluated:

- Local erythema extending beyond suture material or staples
- Induration
- Drainage from surgical incision
- Degree of healing of the surgical incision

Patients with non-healing or worsening status of their surgical site may be considered for additional standard of care treatment, but should be encouraged to remain in the study in order to complete study evaluations.

5.1.2. Serious Interventions

All interventions meeting the following criteria are serious interventions:

- Initiation of antibiotic treatment in patient not previously on antibiotics
- Change in the route of antibiotic administration from oral to intravenous for escalation of treatment
- Change in the type or dosage of antibiotic drug for escalation of treatment
- Readmission (exclusive of readmissions associated with a healed bone site)
- Reoperation (exclusive of reoperations associated with a healed bone site)

5.1.3. Microbiology

The microbiology of the index site will be assessed at baseline and at the time of any subsequent surgical procedure at the index site. The presence of viable microorganisms will

be determined by standard microbiological culture methods and include speciation and antimicrobial susceptibility testing of any bacterial isolates found.

5.1.3.1. Specimen Collection

Samples collected will include at least one tissue site (bone when possible; eraser head size, suitable for dividing into two samples) from the infected bone site (if accessed) or involved tissue adjacent to any implant(s), two swabs of the deep infection site, and two swabs of the superficial tissue/wound closure/sinus tract site. One set of specimens (i.e. 1 tissue specimen, 1 deep swab, 1 superficial swab) will be placed into local site transport vessels. The duplicate set of samples will be placed into transport vessels provided by the central laboratory (International Health Management Associates, Inc.; IHMA). One set of specimens will be delivered to the local site microbiology laboratory using the standard storage and transport procedures employed at each site. The duplicate set of specimens will be transported to IHMA.

5.1.3.2. Specimen Processing: Local Laboratory

The tissue site sample and swabs will be analyzed immediately in the local laboratory for the presence of infectious pathogens by Gram stain and microbiological culture for both aerobic and anaerobic bacteria. The specimens will be processed (primary isolation, identification to species level and susceptibility testing) per the standard methods of each local site microbiology laboratory. Following isolation and identification of each microorganism, the susceptibility of each to one or more standard antibacterial agents (but not including MBN-101), as specified by the surgeon or per local site standard procedures, will be determined. It is recognized that the local site laboratory may be using one of a variety of susceptibility test methods, and therefore, the susceptibility result may be reported as a specific Minimal Inhibitory Concentration (MIC) value or as a categorical result (i.e. Susceptible, Intermediate or Resistant). Susceptibility to MBN-101 will not be determined at the local site laboratory; the susceptibility results determined locally are for the use of the surgeon in the care of the patient.

5.1.3.3. Specimen Processing: IHMA (Central Laboratory)

The tissue site sample and swabs will be analyzed immediately in the central laboratory for the presence of infectious pathogens by microbiological culture for both aerobic and anaerobic bacteria. The specimens will be processed (primary isolation, identification to species level, and susceptibility testing) per the central laboratory methods, as described in the central laboratory study manual.

Following identification, the susceptibility of the isolates to MBN-101 and comparator agents will be determined using either the reference broth microdilution method (for aerobic/facultative bacteria) or the reference agar dilution method (for anaerobic bacteria) as detailed by the Clinical and Laboratory Standards Institute (CLSI). Susceptibility tests for aerobic/facultative bacteria will be quality-controlled as detailed by CLSI using reference quality control strains and previously-established ranges for MBN-101 and comparators. Susceptibility tests for anaerobic bacteria will also include CLSI reference quality control strains, however, since quality control ranges for anaerobic bacteria are not yet established, the MIC values for the quality control strains will be collected then retrospectively compared to the quality control ranges once they are available. Susceptibility testing will be conducted with

batches of study isolates as each study cohort is completed. Patient and specimen identifier and microbiology results will be recorded in the database.

5.1.3.4. Integration of Local Site Laboratory and Central Laboratory Primary Isolation and Identification Results

There may be instances where the organism(s) isolated from a given specimen may be different at the local site laboratory and the central laboratory. In this instance, the central laboratory will first confirm the identification of the archived isolate. If the identification is confirmed, the pathogens present in the specimen will be defined as the total number of pathogens recovered by the local site laboratory and the central laboratory. For example, if the local site laboratory were to recover *S. aureus* and the central laboratory recovered *S. aureus* and *P. acnes*, the specimen would be defined as containing both *S. aureus* and *P. acnes* following merger of the data.

It is possible that local site laboratory may perform susceptibility tests with agents that are also present in the central laboratory test panel. The MIC value (and interpretation) provided by the central laboratory supersedes the local site determination for the purposes of clinical trial data analysis and inclusion in the Clinical Study Report. The local site susceptibility test results are for use by the surgeon in the local care of the patient; however, these data will also be captured in the study database.

5.1.4. Radiographic Evaluation

Radiographic evaluation will be performed at baseline and Weeks 2, 6 and 12. Radiographs (at least two orthogonal views) will be reviewed for bone morphology and integrity, periosteal reaction, union, interval callus formation, loss or change in reduction, and hardware integrity/failure.

5.1.5. Pain Assessments

Pain related specifically to the surgical site (Surgical Site Pain Score) will be assessed via a Visual Analog Scale (VAS, 0-10 scale, where 0=no pain at all and 10 =the worst possible pain) utilizing a 24 hour recall at screening, baseline, Hour 48 and Weeks 2, 6 and 12.

5.1.6. Patient Reported Outcomes

Patient-reported outcomes will be collected using the Veterans Rand 12 Item Health Survey (VR-12) and Short Musculoskeletal Function Assessment (SMFA) at screening, Weeks 2, 6 and 12.

5.1.6.1. The Veterans RAND 12 Item Health Survey (VR-12) Questionnaire

The Veterans RAND 12 Item Health Survey (VR-12) is a brief, generic, multi-use, self-administered health survey comprised of 12 items. The instrument is primarily used to measure health related quality of life, to estimate disease burden and to evaluate disease-specific benchmarks with other populations. The 12 items in the questionnaire correspond to eight principal physical and mental health domains including general health perceptions; physical functioning; role limitations due to physical and emotional problems; bodily pain; energy-fatigue, social functioning and mental health.

5.1.6.2. The Short Musculoskeletal Function Assessment Questionnaire (SMFA)

The 46-item SMFA questionnaire comprises two parts: the dysfunction index with 34 items and the bother index with 12 items. The dysfunction index assesses the patient's perceptions of the amount of difficulty they have in the performance of certain functions (25 items) and how often the patients have difficulty when performing certain functions (9 items). The dysfunction items are grouped into four categories: daily activities, emotional status, function of the arm and hand, and mobility. Each item has a 5-point response format (1 point for good function and 5 points for poor function). The bother index asks the patients to assess how much they are bothered by problems in various areas of life (e.g., recreation, work, sleep and rest). These items also have a 5-point response format (1 point for not at all bothered and 5 points for extremely bothered).

ngg P

Blood samples will be obtained to measure blood concentrations of Bismuth (Bi) as a surrogate for BisEDT. A pre-dose sample will be collected prior to administration of the investigational product. Blood will be drawn for PK samples at nominal 1, 6, 12, 24, 36, 48 (Day 2), 60, 72 (Day 3), 96 (Day 4), and 336 (Day 14) hr after application of MBN-101 to the surgical site.

BisEDT levels in whole blood after MBN-101 administration will be assessed with a qualified Inductively Coupled Plasma Mass Spectrometry (ICP-MS) assay method using bismuth as a surrogate for BisEDT according to the [schedule](#).

ng g P

Safety variables will be collected at regular scheduled intervals during the study as shown in the Schedule of Events ([Table 1](#)). These will include physical examinations, vital signs and laboratory assessments (as detailed below) and the assessment of AEs.

5.3.1. Adverse Events

An adverse event is an undesirable medical occurrence (sign, symptom, or diagnosis) or worsening of a pre-existing medical condition (e.g., diabetes) that occurs after initiation of the investigational study whether or not it is considered to be related to the investigational product. All adverse events (AEs) will be recorded throughout the study, beginning when the subject signs the Informed Consent Form. Adverse events will be coded using the Medical Dictionary for Regulatory Activities (MedDRA, Version 18.1).

5.3.2. Clinical Laboratory Evaluations

All clinical laboratory tests will be performed by the local clinical site laboratory. Blood and urine will be collected for hematology, serology, serum chemistry, urinalysis, and pregnancy testing (as indicated) according to the schedule.

Hematology	WBC, RBC, hemoglobin, hematocrit, platelet count, MCV, absolute neutrophils, absolute lymphocytes, absolute monocytes, absolute eosinophils, absolute basophils, PT, PTT.
Serologies	ESR, CRP.
Serum Chemistry	Sodium, potassium, chloride, carbon dioxide, BUN, glucose, creatinine, total protein, albumin, total bilirubin, direct bilirubin, alkaline phosphatase (ALP), AST (SGOT), ALT (SGPT), GGT, creatinine kinase (CK), calcium, magnesium, Vitamin D.

Other	Urine analysis Serum pregnancy test for women of childbearing potential
-------	--

5.3.3. Vital Signs

Vital signs include blood pressure, pulse, respiratory rate and body temperature; vital signs will be assessed according to the [schedule](#).

5.3.4. 12-Lead ECG

Testing will be conducted at screening, baseline, and 48 hours. The ECG trace will be stored at the investigational sites as source document; clinical interpretation, including normal, abnormal but not clinically significant, and abnormal and clinically significant, will be determined by the investigator.

5.3.5. Physical Examination

A comprehensive physical examination will be performed on all patients at Screening, including assessments of height, weight, head, ears, eyes, nose, throat, chest, heart, abdomen, and skin. Interval physical exams will be performed at all subsequent study visits according to the schedule and will focus on the surgical site, with assessments of local erythema, induration, drainage and degree of healing.

5.4. Prior and Concomitant Medications

All patients will receive their usual concomitant medications for any underlying medical conditions without interruption. Patients will also receive standard of care treatment for their infection that includes systemic antibacterial treatment per prevailing standard of care guidelines (i.e., national, institutional, or physician preference) and other indicated postoperative medications, including pain medications.

Prior and concomitant medications will be coded using the World Health Organization Drug Dictionary (WHO-DD March 2015).

5.5. Medical History

A comprehensive medical history will be taken on all patients at Screening, including but not limited to past medical history, past surgical history, current medications, allergic history and psychosocial history.

6. STUDY ENDPOINTS

6.1. Safety Endpoints

The safety and tolerability of locally administered MBN-101 will be assessed by:

- Treatment-emergent adverse events.
- Treatment-emergent serious adverse events.
- Changes in clinical laboratory tests (clinical chemistry, hematology, and urinalysis).

- Changes in vital signs (blood pressure, pulse, respiratory rate and body temperature).
- Changes in physical exams.
- Clinical findings of 12-lead electrocardiograms.

6.2. Efficacy Endpoints

Clinical activity of locally administered MBN-101 will be assessed by:

- Proportion of treatment failures. A treatment failure defined as a subject with non-healing or worsening status of their surgical site requiring serious intervention by Week 12.
- Cumulative number of serious interventions at Week 12.
- Time to first serious intervention, time to readmission and time to reoperation, exclusive of serious interventions, readmissions, and reoperations associated with a healed bone site.
- Number of subjects undergoing removal of stabilizing orthopedic hardware due to a healed bone site by Week 12.
- Time to removal of orthopedic hardware due to a healed bone site.
- Incidence and intensity of surgical site signs and symptoms, including local erythema, induration, drainage and degree of healing.
- Change from baseline in patient-reported outcomes at each post baseline time point. Patient-reported outcomes will include Veterans Rand 12 Item Health Survey (VR-12) and Short Musculoskeletal Function Assessment (SMFA).
- Surgical site pain score and change from baseline in pain score at each post baseline time point. Pain intensity at the surgical site will be assessed by Visual Analog Scale (VAS, 0-10 scale).
- Findings of microbiology evaluations at the surgical site. Microbiologic success is assessed by clearance of infection.
- Findings of radiographic evaluations at the surgical site. Radiographic success is assessed by healing on radiologic examination.
- Change in serologic markers CRP and ESR at each post baseline time point.

6.3. Pharmacokinetic Endpoints

Whole blood concentrations of Bismuth (Bi) will be measured after administration of single escalating doses of MBN-101 (bismuth as a surrogate for BisEDT) and will be used to calculate pharmacokinetic parameters (i.e., T_{max} , C_{max} , AUC_{0-t} , $AUC_{0-\infty}$, $T_{1/2}$, CL/F , V_z/F).

7. ANALYSIS POPULATIONS

The following analysis datasets will be identified for the purpose of analysis.

pgg **P**

All Screened Subjects will include all subjects who signed informed consent for the study.

pkg **f f** **R b**

Intent-to-Treat (ITT) Population will include all subjects who were randomized in the study. A randomized subject may or may not be treated with the assigned study drug.

pdg

Safety Population will include all subjects who received any amount of study drug (active or placebo). All treated subjects will be included in the safety analysis.

png **P f f a bP**

Modified Intent-to-Treat (mITT) Population will include the ITT subjects who received any amount of study (active or placebo) and have at least one post-treatment assessment. The mITT Population is the primary population for efficacy analysis. Post-treatment assessment includes any post-treatment assessment in any study data collected, for example, lab, vital sign, etc.

png **P**

PK Concentration Population will include all subjects with any measurable bismuth blood concentrations.

ppg **P**

PK Evaluable Population will include all subjects providing sufficient measurable bismuth blood concentrations to facilitate determination of PK parameters.

rg **P**

rgg **P P**

Summary statistics will be presented by treatment group. For continuous variables, the number of observations (n), mean, standard deviation (SD), median, minimum, and maximum will be provided. For categorical variables, the frequency and percentage in each category will be displayed.

For summary statistics, the mean and median will be displayed to one decimal place greater than the original value and the measure of variability (e.g. standard deviation) will be displayed to two decimal places greater than the original value. All Analysis will be performed using SAS® Version 9.3.

All safety and efficacy endpoints will be tabulated with descriptive statistics; data from all placebo subjects (2 per cohort; 6 subjects in total) will be pooled. Data from BisEDT treated subjects will be presented by dose (6 subjects per dose) and combined (a total of 18 subjects). If data permits, differences between the treatment groups and 95% confidence intervals for the difference will be presented.

In the event that a subject received study drug treatment that is not the assigned/randomized

treatment group, the subject has a major protocol deviation. The subject, however, will be included in the analysis for safety and efficacy in the actual treatment group received.

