Patients will be randomized 3:1 (active:control) to three successive doses (0.025, 0.075, or 0.25 mg/mL w:v) of MBN-101 (up to 8 mL, for a dose of up to 0.2, 0.6, or 2.0 mg, respectively) or placebo (diluent). Enrollment to the next dose cohort will not commence until an evaluation by the Data Review Committee (DRC) of all available safety data on all patients through Week 6 of study supports escalation to the next cohort.

PK assessments will be performed predose and at nominal 1, 6, 12, 24, 36, 48 (Day 2), 60, 72 (Day 3), 96 (Day 4), and 336 (Day 14; Week 2) hours after administration of study drug.

Patients will undergo study visits at Hour 48 and Weeks 2, 6 and 12. All patients will be followed for a total of 12 weeks after surgery.

I kg **P**

Twenty-four adult male or female patients meeting protocol-specified eligibility criteria may participate in the study, with the objective of having a total of 6 patients per dose level in the MBN-101-treated group and 6 patients in a pooled placebo-treated group.

I g g

Subjects will be randomized in a 3:1 (active:placebo) ratio up to 24 hours prior to surgery via a central randomization scheme.

I g g

This study is a single blind study; however, knowledge of treatment assignment should remain limited to those directly involved with the patient's surgical procedure and other individuals on a need to know basis. In order to provide unblinding data in an emergency in the absence of an individual privy to treatment assignment, sites will be provided with a numbered unblinding envelope corresponding to each numbered test kit the site is delivered. These envelopes will be securely stored in the pharmacy. The unblinding envelope specifies the treatment group of the kit and should only be opened when absolutely necessary. For treatment of adverse events, it should be assumed that the patient has received study drug, thus avoiding the need to unblind the patient. However, in the event the Investigator determines the randomization assignment information is required to treat the patient for an adverse event, the Medical Monitor should be contacted. If the Medical Monitor cannot be reached, the blind may be broken by opening the envelope. The site should document the unblinding process in the patient's source documents.

I g g **P**

[Table 1](#) presents the schedule of events of the study.

Table 1. Schedule of Events

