8.4. Subject Disposition

Subject disposition will be summarized for the ITT Population for each treatment group and in total. The following subject disposition categories will be included in the summary for all randomized subjects:

- Subjects who were randomized,
- Subjects who were treated,
- Subjects who were not treated,
- Subjects who completed the study, and
- Subjects who did not complete the study.

SAP MBN-101-201
Version 1.0, 19 July 2018

For subjects who did not complete the study, a summary will be provided by reason for discontinuation. The total number of subjects in each defined analysis population will be tabulated.

In addition, a summary of screen failures and the reason will also be tabulated for All Screened Subjects.

rgg **P** **P**

Demographic and baseline characteristics such as age, age group (<65 and \geq 65), gender, race, ethnicity, height, weight, BMI, and surgery site characteristics (type of injuries, method of fraction fixation, surgical site location), time from previous surgery to study enrollment, and type of previous treatment and current surgery characteristics (area of the osteosynthesis or osteomyelitis site, hardware removal, new hardware replacement, and method of wound closure) will be summarized with appropriate descriptive statistics (the number of observations, mean, standard deviation, median, minimum and maximum for continuous variables; number and percentage for categorical variables) by treatment group and overall.

Baseline characteristics summaries will be based on the Safety Population and repeated for the mITT and PK Concentration Populations.

rgg **P**

Distribution of Pathogens Isolated at Baseline will be tabulated by treatment group and overall for the mITT Population with any baseline pathogens.

rgg **P**

Medical History (Connective tissue disease/Autoimmune disease, HIV/AIDS, Renal disease, and Diabetes Mellitus) will also be summarized descriptively by treatment group and in total for the Safety and mITT Populations.

All medical histories will be listed by subject.

rgg **P** **P**

Prior medications are medications used before the first dose of study drug. Concomitant medications are medications that were taken on or after first dose of study drug.

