The prior and concomitant medications will be summarized with the number and percentages by ATC class and preferred term for each treatment group and overall for the Safety and mITT Populations. Concomitant systemic antibiotic administered for treatment of the infected osteosynthesis/arthrodesis surgical site will also be summarized in the same manner. Although a subject may have taken two or more medications, the subject is counted only once within an ATC classification. The same subject may contribute to two or more preferred terms in the same classification.

All prior and concomitant medications and procedures will be listed by subject.

rgg **P**

All efficacy analysis will be based on the mITT Population.

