8.9.1. Treatment Failure

The number and percent of subjects with treatment failure during the study will be tabulated by treatment group. If data permit, the difference in proportion of treatment failures between each treatment dose group and placebo group and the corresponding 95% exact confidence intervals for the difference will be presented. The Exact confidence interval will be calculated using the Clopper Pearson method.

Sensitivity Analysis for Treatment Failure

An 'as assigned' analysis will be performed on the mITT subjects as a sensitivity analysis for treatment failure. In this analysis, subjects who received a treatment that is not the assigned treatment will be included in the 'assigned' treatment group for this analysis.

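### Misallocated subjects are grouped by treatment received for efficacy as well as safety, and an as-assigned check is planned for only one efficacy endpoint

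*SAP*

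**What the plan says.** Section 8.1 treats receipt of the wrong treatment as a major protocol deviation and keeps the subject in the analysis, "included in the analysis for safety and efficacy in the actual treatment group received". The one rule covers both safety and efficacy.

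Section 7.4 states that "The mITT Population is the primary population for efficacy analysis", and section 8.9 repeats it without exception: "All efficacy analysis will be based on the mITT Population". The mITT definition sets out who is included (randomised, treated, at least one post-treatment assessment). It does not say which group label applies, so the 8.1 rule governs.

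Assignment is used for grouping in one place, section 8.9.1: "An 'as assigned' analysis will be performed on the mITT subjects as a sensitivity analysis for treatment failure". Sections 8.9.2 to 8.9.9 contain no such analysis. The ITT set is defined ("Intent-to-Treat (ITT) Population will include all subjects who were randomized in the study") and is used for disposition ("Subject disposition will be summarized for the ITT Population for each treatment group and in total"), but no efficacy analysis uses it.

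**The concern.** Grouping by treatment received is the usual choice for safety, where the question is what exposure did. For efficacy, the placebo group is informative because chance decided who was in it. Moving a subject after allocation lets something other than chance determine group membership, and the usual rule is therefore to group by assignment.

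The SAP does plan comparisons that depend on this. Differences from placebo with 95% intervals are specified for treatment failure (8.9.1), for serious interventions, readmission and reoperation (8.9.2), for surgical site signs and symptoms (8.9.4) and for microbiological success (8.9.7). Section 8.1 adds a general provision for such differences where the data allow. Only the first of these has an as-assigned counterpart, and the SAP gives no reason for stopping there. At 6 subjects per group, one relabelled subject can visibly change a table.

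**Working it through.** **The plan's own figures.** The SAP gives no figure for misallocation. Its only design calculations are in section 4 and concern adverse events: 1 − (1 − 0.385)^6 = 0.946 and 1 − (1 − 0.153)^18 = 0.950, against a stated 95%. They reproduce approximately and do not enter this point.

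**Inputs.** There are 6 subjects per dose and 6 pooled placebo, 2 from each cohort (sections 3 and 8.1). The planned contrast is each dose minus pooled placebo (8.9.1, 8.9.2, 8.9.4, 8.9.7). *Assumption:* exactly one subject assigned to a dose receives placebo. Let a and b be the as-assigned event counts on dose and placebo.

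**Step 1, one proportion.** The dose group falls from 6 to 5. The largest change is from 1/6 to 0/5, or from 5/6 to 5/5: 1/6 = 16.7 points. The placebo group rises from 6 to 7. Its largest change is from 0/6 to 1/7, or from 6/6 to 6/7: 1/7 = 14.3 points.

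**Step 2, the difference.** The as-assigned difference is a/6 − b/6.

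- The crossover subject has no event: as received the difference is a/5 − b/7, so the shift is a/30 + b/42.
- The crossover subject has an event: as received it is (a − 1)/5 − (b + 1)/7, so the shift is a/30 + b/42 − 12/35.

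**Step 3, range over all possible counts.**

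| Case | Extreme counts | Shift |
|---|---|---|
| No event | a = 5, b = 6 | 5/30 + 6/42 = +31.0 points |
| Event | a = 1, b = 0 | 1/30 − 12/35 = −31.0 points |

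The smallest shift is 0 (a = b = 0, no event). A placebo-assigned subject who receives a dose gives the same bounds, with the roles exchanged.

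**Step 4, illustration with assumed counts.** As assigned, 2/6 against 2/6 is a difference of 0. If the crossover subject failed, the as-received difference is 1/5 − 3/7 = −22.9 points. If not, it is 2/5 − 2/7 = +11.4 points.

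**Step 5, knock-on effect.** All three doses share the placebo pool, so a crossover into or out of it changes all three contrasts. In the two contrasts whose dose group is unaffected, only the placebo term moves: by up to 1/7 = 14.3 points when the pool grows to 7, or 1/6 = 16.7 points when it shrinks to 5.

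**Step 6, no misallocation.** Assigned and received groups are then the same, and every shift is 0.

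**Step 7, what assignment would protect.** Cohorts are enrolled in succession, and within each the allocation is random: "Subjects will be randomized in a 3:1 (active:placebo) ratio up to 24 hours prior to surgery via a central randomization scheme". For any one dose, 2 of the 6 pooled placebo subjects were randomised alongside it and 4 of 6 came from other cohorts. Grouping by assignment restores the within-cohort element only.

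**The case against.** The strongest reply is that this is a contingency in a small descriptive trial. The 31.0 points are a worst case, conditional on an event whose frequency the SAP does not state. There are 24 subjects, one application each, central randomisation and numbered kits. The primary objective is safety, no hypothesis is tested, and for activity by dose a grouping by dose actually given can be defended as exploratory. Treatment failure already has its as-assigned check. All of this stands and sets the severity. It does not make the rule the better choice, since a misallocation rule matters only when a misallocation happens.

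A reader might infer four stronger things that the SAP does not support.

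- *That the efficacy comparisons in general fail to preserve randomisation because of this rule.* The rule has no effect without a misallocation. The contrast with pooled placebo is also partly non-concurrent whichever grouping is used. The mITT set further omits randomised subjects who were untreated or never assessed after treatment, so even an as-assigned analysis in it is not a full ITT analysis.
- *That surgical staff who know the assignment would depart from it selectively.* The SAP limits knowledge of assignment to those directly involved in the surgery and others who need to know. It does not say that they choose the kit or can deviate from it. Non-random deviation is possible, but it is not documented.
- *That the mITT label conceals the grouping.* Section 8.1 states the rule openly and 8.9.1 names the alternative. The label is unconventional but the passages are consistent.
- *That the change merely swaps two analyses already planned.* That is true only for treatment failure.

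**Conclusion.** The point holds as a weakness in a stated rule, at low severity. For efficacy, section 8.1 should not move a misallocated subject out of the assigned group, and the single as-assigned sensitivity analysis leaves the other endpoints without a check.

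One crossover among groups of 6 can shift one proportion by up to 16.7 points and a dose-minus-placebo difference by anything from 0 to 31.0 points in either direction. These are bounds over all possible counts, assuming one crossover between a dose and placebo with every subject evaluable. They do not estimate expected bias, because the SAP gives no misallocation rate. Sample size is unaffected.

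**What to change.** In section 8.1, split the rule: safety by treatment received, and all efficacy endpoints by assigned treatment within the mITT set. In section 8.9.1, make the as-received analysis the sensitivity analysis for treatment failure.

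The cost is SAP wording and the grouping variable in the efficacy tables, with no new data. For treatment failure the two planned analyses change places. For the other efficacy endpoints the as-assigned analysis replaces the only one planned, so the SAP can add that an as-received table will be supplied for those endpoints if a misallocation occurs. The change is best made before any misallocated subject's outcome is known to those writing the rule. It leaves the partly non-concurrent placebo pool and the mITT exclusions as they are, and the text should not claim otherwise.
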